10.2 Informed Consent and inclusion/exclusion criteria

The Investigator or designee will ensure that each subject and/or subject’s parent/legal guardian is given full and adequate oral and written information about the nature, purpose, possible risks, and

Dipartimento Area Materno - Infatile

SC NEFROLOGIA E DIALISI PEDIATRICA – TRAPIANTI DI RENE – Direttore: [name]

[contact]

email: [contact]

benefits of the study. Subjects/parents/legal guardians will be notified that they are free to discontinue participation in the study at any time and will be given the opportunity to ask questions and allowed time to consider the information provided. After informed consent and assent (as appropriate) is obtained, subjects will undergo enrollment assessments. Once it is determined that they are eligible for the study, they will be enrolled in the study and baseline assessments will be completed. A copy of the signed ICFs will be provided to the subject and/or subject's parent/legal guardian.

10.3 Demographic data

Demographic data (age, sex, and ethnicity, appearance age) and response to therapy will be collected for all participants during the enrollment visit.

10.4 Medical history

Medical history will be recorded at enrollment visit. Investigators should document the occurrence, signs, and symptoms of the participant's preexisting conditions, including all prior significant illnesses. A detailed medical history about disease indication will be requested and will include prior surgeries, renal biopsies, hospitalizations, dialysis, transplantation, laboratory data, and extrarenal manifestations of the disease. Available disease medical history for the 3 years preceding screening will be requested.

10.5 Physical examination

A physical examination, performed by the investigator or designee, will include, at a minimum, assessment of the following: general, head, ears, eyes, nose, throat, heart, chest, lungs, abdomen, skin, extremities, back/neck, musculoskeletal, and lymph nodes. Additional symptom-driven physical examinations may be performed at any time, as deemed necessary by the investigator. See the schedule of assessments for the details regarding at which visit physical examination will be performed.

10.6 Assessment of oedema

Edema will be assessed at enrollment, 6-week visit, 12-month visit and at the first relapse. Assess for peripheral edema by pressing the area firmly with the thumb or index finger for 5 seconds and then release.

10.7 Vital signs

Vital signs including height, weight and systolic and diastolic blood pressure measurements will be evaluated at the visits indicated in the schedule of assessments.

10.8 Routine laboratory tests (local laboratory)

Blood samples. Blood samples for clinical assessments will be collected at the visits specified in the

Dipartimento Area Materno - Infatile

SC NEFROLOGIA E DIALISI PEDIATRICA – TRAPIANTI DI RENE – Direttore: [name]

[contact]

email: [contact]

schedule of assessments. The following analytes will be measured: BUN, sCr, albumin, Na, K, total cholesterol, triglycerides, IgG, IgM, IgA and serum complement 3 (C3). These exams will be conducted at each recruiting site.

Urine samples. Urine for clinical assessments will be collected at the visits specified in the schedule of assessments. The following analytes will be measured: urine protein/creatinine ratio, and urinalysis. These exams will be conducted at each recruiting site.

10.9 Sample collection for molecular analysis

The following samples are needed:

1. Blood sampling: for INS patients and controls, two additional aliquots of blood (a maximum of 10-12 mL at a single time; body weight >12 kg) based on the patient's age and clinical condition during the sampling will be collected in the occasion of routine laboratory tests.
2. Urine sampling: spot urines (20-30 mL) from residual urine from routine laboratory tests.

Detailed sample processing:

- **Whole blood.** Blood collection for genetic and epigenetic will be performed for all NS patients recruited into the study. Whole blood will be collected and stored at 4°C for analysis. Shipment of samples will be done at 4°C.
- **Mononuclear cells from peripheral blood.** Whole blood will be isolated using the BD Vacutainer® CPT™ Mononuclear Cell Preparation Tube. Peripheral blood mononuclear cells (PBMCs) will be isolated by Ficoll procedure followed by washing step with PBS, and freezed in Cell Storage Media at density of 10^6 cells/vial and stored in liquid nitrogen or -80°C. Shipment of samples will be done by dry ice.
- **Urine.** Urine samples will be centrifuged at 3,000 g for 15 minutes to remove large membrane fragments and other debris. A protease inhibitor cocktail will be added immediately (PI inhibitor). Urine aliquots will be stored at -80°C. Shipment of samples will be done by dry ice.
- **Serum.** The serum will be obtained by direct cascade activation of coagulation from whole blood. The blood will then be centrifuged at 3,000g for 20 minutes to remove corpuscular components along with clots and debris. Serum aliquots will be stored at -80°C. Shipment of samples will be done by dry ice.

Urine and serum will be centralised at Heidelberg University Hospital. The storage of peripheral blood mononuclear cells (PBMCs) will be centralized at the coordinating centre.

Any residues of biological material that will not be used for the study will be eliminated at the end

Dipartimento Area Materno - Infatile

SC NEFROLOGIA E DIALISI PEDIATRICA – TRAPIANTI DI RENE – Direttore: [name]

[contact]

email: [contact]

of the study.

11. Detailed technical methodologies

Exome sequencing (collaborator involved: Medical University Gdansk). DNA samples extracted from blood leukocytes will be subject to sequencing using TruSeqExome Enrichment Kits according to the manufacturer's instructions (Illumina). Data analysis will be carried out as previously described (11).

Whole-Genome Bisulfite Sequencing Method (collaborator involved: University of Istanbul). For epigenetics analysis on CD45 lymphocytes, 5 µg of genomic DNA (OD260/280: 1.8–2.0) will be used as starting material. Bisulfite treatment of genomic DNA will be performed, and non-methylated cytosine nucleotides will be converted to uracil and read as thymine (T) when sequenced. Methylated cytosines protected from conversion are still read as cytosine. The EpiGnome libraries will be diluted and loaded onto the cBot DNA Cluster Generation System. After cluster generation, the flow cell will be transferred to the HiSeq 2500 System for sequencing using 75 bp paired-end reads. The HiSeq 2500 generates approximately 500 Gb of sequence data per flow cell or about 62 Gb per lane allowing a coverage of approximately 120 Gb of data per sample. Additional sequencing can be completed for higher coverage. Data analysis of whole genome bisulfite sequencing will be conducted. FastQC tool will be used to check the raw data quality. Alignment will be done with the Bismark tool to identify the methylated regions (methylation calling). Statistical analyses will be performed with a methyl Kit.

Cytofluorimetric analysis (collaborator involved: the University of Milano). Purified PBMCs will be discriminated by incubation with the dead cell Stain Buffer (BD) and surface staining will be then performed at 4°C for 20 min. Cells will be then fixed and permeabilized, stained at room temperature for 20 min with antibodies against intracellular antigens. For cell activation and intracellular cytokines staining, PBMCs will be stimulated with PMA/Ionomycin (1 µg/mL) for 2 hours. Brefeldin A (10 ng/mL) will be added as a protein transport inhibitor. Cells will be stained with Fixable Viability Stain 780 (BD) followed by cell-surface marker (BD Pharmingen) and analyzed with the BD FACS Symphony flow cytometer.

Single cell RNAseq experiments combined with CITE-seq (collaborators involved: IRCCS Ca' Granda Ospedale Maggiore Policlinico and the University of Milano). CD3+ and CD19+ cells from peripheral blood will be sorted from purified PBMCs. CD3+ cells will be labeled using barcoded versions of anti-CD4 and anti-CD8 (TotalSeqC – Biolegend). After cell number and viability determination by automated cell count, the appropriate volume of CD3+ and CD19+ cells will be loaded onto a 10x Genomics chip to recover 10.000 cells/sample. RNA-Seq and single-cell repertoire analyses will be performed according to 10x Genomics 5' V(D)J protocol. Library sequencing will be performed using the Illumina NovaSeq 6.000 (Eurofins facilities, <https://eurofinsgenomics.eu/en/custom-dna-sequencing/>).

scRNA-Seq data analyses (collaborators involved: IRCCS Ca' Granda Ospedale Maggiore

Dipartimento Area Materno - Infatile

SC NEFROLOGIA E DIALISI PEDIATRICA – TRAPIANTI DI RENE – Direttore: [name]

[contact]

email: [contact]

Policlinico and the University of Milano). Raw fastQ files will be aligned to the human reference genome GRCh38, subjected to quality control filtering, and data normalization high variable genes will be identified and used in a principal component analysis (PCA). Downstream analyses of scRNAseq data on different unsupervised algorithms (UMAP, tSNE) will allow the spatial visualization of the single-cell dataset and features. T- and B- cell clusters will be defined using the Leiden algorithm, and differentially expressed genes (DEGs) between distinct cell clusters and experimental groups will be identified (P value ≤ 0.05 , log2 fold change ≥ 1.5). The procedure will generate an enrichment in immune cell subsets with a specific molecular signature that will be analyzed bioinformatically. Gene Ontology (GO) analyses will also be performed. For scTCR-seq and scBCR-seq data analysis, CDR3 sequences and V(D)J gene rearrangement will be obtained using the Cell Ranger VDJ 10X pipeline. T/B cells showing consistent CDR3 amino acid sequence will be defined as clonotypes.

EV isolation and characterization (collaborator involved: the University of Milano). Purification of EVs will be obtained by size exclusion chromatography using 70 nm qEV columns (IZON) after a 100 kDa centrifugal filter (Sartorius). The concentration and size distribution of EVs will be measured using NanoSight LS300 (NanoSight Ltd). EVs integrity will be characterized by transmission Electron microscopy (TEM) by adherence to glow-discharged formvar-coated copper grids 300 mesh.

Single vesicles studies (collaborator involved: the University of Milano). EV evaluation at single levels will be performed following the pipeline described by (12). Super-resolution microscopy will be performed using the Nanoimager S Mark II microscope from ONI (Oxford Nanoimaging, Oxford, UK) equipped with a 100X. Tetraspanins and selective markers will be tested using the Apex Antibody Labelling Kit (Invitrogen) according to the manufacturer's protocol. Samples will be also analyzed with ExoView Plasma Tetraspanin kit on an ExoView R100 instrument (NanoView Biosciences) following the manufacturer's instructions.

EV protein corona and lipid evaluation (collaborator involved: the University of Milano). EVs surface phenotype will be analyzed using the MACSplex kit (Miltenyi Biotec) on a BD FACSCanto II (Becton Dickinson) as (12). Proteomic studies will be then performed by two-dimensional difference gel electrophoresis (2D-DIGE) followed by liquid chromatography-tandem mass spectrometry (LC-MS) as (13). Surface proteins will be separated from the ones from the lumen. Lipidomic profile will be also evaluated by gas chromatography (GC)-MS.

Proteomics and phospho-proteomics (collaborator involved: Cologne University Hospital). For expression profiling and characterization of cellular phosphor-proteomes, a fully established standard pipeline at the Cellular Stress Responses in Aging-Associated Diseases and the Centre for Molecular Medicine Cologne will be used. Proteins are purified, alkylated, and digested. Peptides are purified after acidification by a Stage-Tip protocol using an SDB-RPS-Matrix (Styrene Divinyl Benzene reverse phase sulfonate-Matrix and measured in a Q Exactive Plus Tandem or a LTQ Orbitrap XL spectrometer. Raw data is processed using the MaxQuant software, is compared to reference datasets, and is analyzed and displayed using Perseus software. To obtain insights into the

Dipartimento Area Materno - Infatile

SC NEFROLOGIA E DIALISI PEDIATRICA – TRAPIANTI DI RENE – Direttore: [name]

[contact]

email: [contact]

activation of specific signaling cascades by posttranslational modification (phosphorylation) we will also characterize the phospho-proteome. Phosphorylated peptides are enriched after standard isolation and purification with a special kit (High-Select Fe-NTA Phospho-peptide Enrichment Kit). For an unbiased serum proteomics approach, we can rely on the established fully automated clinical pipeline using liquid handling robots and state-of-the-art mass spectrometry platforms, including the latest generation Orbitrap Exploris 480. The approach enables the detection and quantification of on average 300 plasma/serum proteins per hour using a data-independent acquisition approach from a 5 µl sample volume.

12. Source Documents

Medical history and all clinical data collected during the study will be collected from each visit's medical records.

Local laboratory records will be used to collect laboratory analysis results.

13. Sample Size

As this is a descriptive and explorative study without inference in the primary endpoint, and given the incidence of childhood idiopathic nephrotic syndrome, which is considered a rare disease, the number of recruiting centers, we foresee enrolling in this study 110 treatment-naïve INS children. A homogeneous age control group of healthy children undergoing minor urological surgical corrections will be enrolled as a control group (n=40 children in 3 years). These numbers are the maximum we can recruit, but at the same time, we think that this study could serve as an important basis for appropriate studies in the future.

14. Data Management

A consortium was created under the direction of the Lead Unit (IRCCS Ca Granda of Milano, [name], Proposal Coordinator) with the Partners involved in the study. At the enrollment visit, a unique code will be assigned to each participant. The de-identification of the data will take place in such a way that people who access the database will not be able to trace the identity of the subjects in any way. Only local investigators will be able to trace the identity of the enrolled subjects.

The data necessary for the study will be recorded in a specific eCRF in a Data Management System validated according to national legislation, provided by the Scientific Management of the Foundation. The platform used will be RedCap (Research Electronic Data Capture).

The REDCap Consortium is made up of >1000 institutional partners around the world (research institutions, universities, ministries, etc.). The consortium supports a secure web application (REDCap) designed exclusively to support data capture for research studies. The REDCap application allows users to create and manage online databases quickly and securely and is currently in use for more than 110,000 projects with approximately 150,000 users covering numerous areas of research interest across the consortium.

Dipartimento Area Materno - Infatile

SC NEFROLOGIA E DIALISI PEDIATRICA – TRAPIANTI DI RENE – Direttore: [name]

[contact]

email: [contact]

Through REDCap, for this study the following will be implemented: a) identification at user level, with specific restrictions based on role in the study b) validation and control of data integrity in real time c) de-identification of patients before data export d) centralized data storage with daily backup, a secure server within the Foundation's IT structure.

15. Statistical analysis

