8.3. Secondary endpoints

Related to secondary objective 1:

- 1- Genetic kidney- and immune-related risk factors measured as number of variants in kidney- and immune-related genes, associated to INS incidence, progression, and poor response to therapy.
- 2- A methylation profile of target genes measured as number of hypomethylated and hypermethylated immune-related gene regions, related to a faster progression to kidney failure and altered immune profile.

Related to secondary objective 2:

- 3- Difference in terms of % and absolute number of subpopulations of B cells and T cells among patients classified as SRNS/SDNS, IRNS, and healthy children.
- 4- Changes in immune cell subsets genes, expressed as the number of expressed genes per cell (log-transformed Unique Molecular Identifier counts, UMI), among patients classified as SRNS/SDNS, IRNS, and healthy children.
- 5- Signaling dynamics changes, measured as number of phosphosites for each target protein expressed in the subpopulation of primary B and T cells, implicated in the development of kidney damage in INS.

Related to secondary objective 3:

- 6- Difference in the urine EV concentration expressed as total number/urine creatinine levels, and size as mean diameter, among patients classified as SRNS/SDNS, IRNS, and healthy children.
- 7- Difference in the urine and serum EV surface proteome phenotype, in terms of the ratio of the average of label-free quantification intensities for each detected EV protein, among patients classified as SRNS/SDNS, IRNS, and healthy children.

Dipartimento Area Materno - Infatile

SC NEFROLOGIA E DIALISI PEDIATRICA – TRAPIANTI DI RENE – Direttore: [name]

[contact]

email: [contact]

8- Difference in the serum proteome, in terms of the ratio of average of label-free quantification intensities for each detected protein, among patients classified as SRNS/SDNS, IRNS, and healthy children.

Related to secondary objective 4:

9- To describe different molecular signatures (characteristics) for healthy children group in the same way done for the primary endpoint.

9. Enrollment and inclusion/exclusion criteria

The recruiting centers that will be involved in the study are listed in Appendix 1.

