1. Due to the nature of the pathology (rare disease), one of the risks could be not reaching the number of recruited patients (annual incidence of 2-7/100,000 children). Our contingency plan will be the integration of additional ERKnet and ESCAPE Network centers through an addendum to the protocol.
2. The other limitation could be the absence of sample stability. Our contingency plan will be to define specific isolation workflow protocols, centralize the biobanking system, and perform sample stability tests for the different applications.
3. Another problem could be a difficult blood draw based on the age of the new-onset children recruited in the study. We will exclude Infantile N from the study to overcome this problem.

From the statistical side, all the data will be extensively scrutinized to ensure that misreporting is minimized. Potential confounders will be identified and assessed routinely throughout the analysis. Where possible, confounding factors will be adjusted for in the analysis. Where < 10% of missing data are present in a variable we will aim to impute missing data from other available data sources using a random Forest regression or classification approach. Variables with >20% missing values within a group will be kept aside and used only for descriptive quantitative evaluations. Statistical analysis using linear mixed effect models will ensure that data from the same individuals over time are properly considered.

18. Other aspects

The study will be conducted by the Standards of Good Clinical Practice, the ethical principles deriving from the Declaration of Helsinki.

The study and the related documentation will be presented to the competent Ethics Committee of each center. The study will begin only after receiving the authorizations requested according to the institution's internal procedures.

The Ethics Committee must also approve any changes to the protocol and advertising used to recruit subjects for the study, according to local regulations.

18.1 Informative note to subjects and consensus module to personal data treatment.

The investigators have the responsibility to obtain a signed informed consent by parents or legal

Dipartimento Area Materno - Infatile

SC NEFROLOGIA E DIALISI PEDIATRICA – TRAPIANTI DI RENE – Direttore: [name]

[contact]

email: [contact]

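### Methylation is measured in unsorted CD45 cells and the stated two-group tests are unadjusted, so endpoint 2 could in part reflect the B- and T-cell differences that endpoint 3 tests for

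*Protocol*

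**What the plan says.** **Material and software.** Section 11 (whole-genome bisulfite sequencing) gives the material with the words "For epigenetics analysis on CD45 lymphocytes" and an input of 5 µg genomic DNA. It then says "Statistical analyses will be performed with a methyl Kit". It describes no separation into B cells, T cells or subsets, no deconvolution and no covariate.

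**Endpoint 2 (section 8.3).** The methylation profile of target genes is "measured as number of hypomethylated and hypermethylated immune-related gene regions, related to a faster progression to kidney failure and altered immune profile".

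**Endpoint 3 (section 8.3).** "Difference in terms of % and absolute number of subpopulations of B cells and T cells among patients classified as SRNS/SDNS, IRNS, and healthy children".

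**Tests.** Section 15.2 assigns two-group differences, across all analyses, to a t-test or a Mann-Whitney test. Neither takes covariates. Where features outnumber samples it allows LASSO or feature selection.

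**Confounding.** Section 17 says: "Where possible, confounding factors will be adjusted for in the analysis". It mentions neither cell composition nor the cytometry data.

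**Timing.** Schedule A places the blood for genetic analysis at enrolment only. The mononuclear-cell sample is taken at enrolment and again at 6 weeks, 12 months and first relapse. Section 10.9 groups genetic and epigenetic blood together, collects it as whole blood and describes it for nephrotic syndrome patients. Schedule B lists no genetic blood sample for controls.

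**The concern.** A methylation level read from bulk DNA is an average over the cells in the tube, weighted by their proportions. It moves when methylation changes inside cells, and it also moves when the proportions change. Only the first is an epigenetic modification in the sense of secondary objective 1, which seeks modifications that take part in the pathogenesis.

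The protocol has reason to look for the second. Its rationale (section 6) cites T-cell imbalance and B-cell involvement, and endpoint 3 tests for differences in cell fractions. Yet the fractions appear only as an outcome and nowhere as an input to the methylation analysis. A region that separates the groups only because one group has more B cells would enter the endpoint 2 count. Relating that count to an altered immune profile would then be partly circular.

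At stake is the interpretation of endpoint 2, and of the genetic/epigenetic component that section 8.2 lists beside immune status in the signature meant to discriminate SRNS/SDNS from IRNS.

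**Working it through.** The protocol gives no effect size, power or threshold for methylation, so there is no figure of its own to reproduce. What follows is an illustration.

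**Inputs**
- From the protocol: 110 incident patients (section 13) and a significance level of 0.05 (section 15.2; two-sided assumed).
- Assumed, not in the documents: B-cell fraction with mean 15% and SD 6 points; group split 33/77 or 55/55; between-cell methylation contrast of 40 or 80 points; 30 or 300 reads per region; cytometry error of 1 point; group shift in B-cell fraction of 0, 2.5, 5 or 10 points.

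**Step 1: size of the artefact.** Let *f* be the B-cell fraction, *m_B* the methylation of a region in B cells and *m_O* its methylation in all other cells. Bulk methylation is *m_B·f + m_O·(1 − f)*. If *m_B* and *m_O* are the same in both groups, the bulk difference between groups is *(m_B − m_O)·Δf*:

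- 0.40 × 0.05 = 0.02, or 2 points
- 0.40 × 0.10 = 0.04, or 4 points
- 0.80 × 0.05 = 0.04, or 4 points
- 0.80 × 0.10 = 0.08, or 8 points

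**Step 2: how often a test would flag it.** Data were simulated with no methylation change inside any cell, with 4,000 runs per scenario. Each region was tested with an unadjusted t-test and with a linear model that included the measured B-cell fraction. Ranges are over split, contrast and read depth.

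| Shift in B-cell fraction | Unadjusted rejection |
|---|---|
| 0 points | about 5% |
| 2.5 points | 11–47% |
| 5 points | 28–97% |
| 10 points | 74–100% |

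With the fraction as covariate, rejection was 4.6–7.1% over all scenarios. The error assumed in the measured fraction leaves some confounding, which explains values slightly above 5%.

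**Step 3: relation to endpoint 3.** With 110 patients and the same two splits, power to detect a difference in cell fraction is 30–35% at a standardised difference of 0.3, 67–75% at 0.5 and 97–99% at 0.8. With the assumed SD of 6 points, a 5-point shift is 5/6 = 0.83 SD. A shift that endpoint 3 is well placed to find is therefore also one that can produce apparent differential methylation at regions that distinguish cell types.

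Step 2 applies the section 15.2 t-test to one region at a time. It does not model methylKit, LASSO or any minimum-difference cutoff. A cutoff would reduce the number of regions affected.

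**The case against.** **The covariate list belongs in the SAP, and section 17 already promises adjustment.** This is the strongest objection. A variable can be both an endpoint and a covariate, and nothing bars an analyst from adjusting. It stands in so far as an SAP could solve the problem. But the protocol does more than stay silent: it fixes unsorted material and states unadjusted two-group tests. The section 17 sentence is conditional and does not identify composition.

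**Section 15.2 may not govern methylation.** Methylation has its own software, and settings with more features than samples go to LASSO or feature selection. This stands as a limit on the rejection rates in Step 2. It does not touch Step 1, because any method applied to bulk values without the fractions meets the same shift.

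**Endpoint 2 does not name the SRNS/SDNS versus IRNS contrast.** Correct. That contrast is taken from section 8.2, where epigenetic background is among the features meant to discriminate the groups. Endpoint 2 itself refers to progression and immune profile, so association with composition may be part of what is sought. This is a good reason to report both counts.

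**Stronger readings that a reader might infer.** One is that endpoint 3 presupposes a difference in fractions. It tests for one and states no expected size. Another is that endpoint 2 merely restates endpoint 3, so that the signature counts one signal twice as independent evidence. No section treats the two as independent evidence. Correlated predictors do not by themselves invalidate a predictive model, and section 13 calls the study descriptive and explorative.

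**The cytometry fractions may not match the sequenced cells.** This stands. Epigenetic blood is whole blood stored at 4°C, whereas cytometry uses isolated and frozen mononuclear cells. Section 11 does not say how the CD45 cells are obtained or what else the isolate contains.

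**Conclusion.** The point holds as a correctable weakness in how endpoint 2 is analysed. If B- or T-cell fractions differ between SRNS/SDNS and IRNS, regions whose methylation differs between cell types can be counted as hypo- or hypermethylated with no change inside any cell. Endpoint 2 could then in part reflect endpoint 3. The 2 to 8 point range in Step 1 rests on assumed contrasts and shifts. It shows that the mechanism can matter, not how large it will be here.

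Two conditions must both be met: the fractions differ between groups, and the region distinguishes cell types. Where either fails, there is no bias from this source. The point applies mainly to the comparison among patients, because Schedule B lists no genetic blood sample for controls. It does not call the predictive aim of the primary objective into question.

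**What to change.** 1. State in section 11 how the CD45 cells are isolated and which cell types the isolate contains.
2. Include the enrolment flow-cytometry fractions (B cells and T cells, with subsets where available) as covariates in the methylKit differential-methylation model.
3. Report the number of hypo- and hypermethylated regions with and without this adjustment, and read only the adjusted count as evidence of epigenetic change beyond cell mix.
4. If the isolate contains cells other than the lymphocytes measured in the mononuclear-cell sample, say that the correction is partial.

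**Cost.** A short addition to the protocol or SAP. Schedule A already takes both samples at enrolment, so no new visit or blood draw is needed. Fewer regions may remain after adjustment, and the adjusted analysis removes some signal that accompanies genuine lineage shifts. The unadjusted count, reported beside it, keeps that signal visible.
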